5.3.1 Unscheduled Assessments

Both scheduled and unscheduled assessments, including early termination visits, will be considered for planned timepoint summaries. All assessments will be presented in data listings.

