### **3.2.6 Week 12 (End-of-Study/Early Termination [EOS/ET])**

- Physical examination
- Vital signs (sitting [at least 3 minutes] blood pressure, pulse, respiratory rate, and temperature)
- Weight
- 12-lead ECG (single recording)
- Laboratory profiles (hematology, serum chemistry, and urinalysis [if able])
- Urine pregnancy test for all women of childbearing potential
- Blood sampling for PK assessments
- CMAI
- ZBI
- NPI-C (complete)
- MMSE
- mADCS-CGIC
- KSS
- ADCS-ADL
- Assessment of concomitant medications/treatments
- Assessment of AEs
- GCAS
- Study drug accountability

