### **6.3 Pharmacokinetic Assessments**

Blood samples will be collected via venipuncture at the Baseline visit (pre-dose), and at Weeks 2, 4, and 12 (EOS/ET) for plasma concentration measurements of pimavanserin and its metabolite (AC-279). (Note: If collection at Week 2 does not occur, then collection should be attempted at Week 8.) In addition, if possible, blood samples will be collected from subjects who experience an SAE or an AE leading to discontinuation, as soon as possible after experiencing the event.

For all PK samples (scheduled and unscheduled), the actual dates and times of administration of the last 3 doses of study drug before PK sample collection will be recorded on the CRF, if known. For samples collected from subjects who experience an SAE or an AE leading to discontinuation, the date and time of the last dose prior to the SAE or AE should also be recorded.

Blood samples will be processed for determination of pimavanserin serum concentrations. At each timepoint, blood will be collected, processed, and serum samples will be shipped to the central laboratory for storage and to the bioanalytical laboratory for analysis. A laboratory manual will be provided for sample processing, storage, and shipping procedures. Plasma concentration data will not be analyzed until the official unblinding of the clinical database at the end of the study.

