- a. Study visits are designated by weeks and have a ± 3 -day window (Visits 2 through 5) or a $+7$ -day window (Visit 6) calculated from the Baseline Visit (Day 1). Clinic visits may be split over multiple days within the specified windows, if necessary.
- b. The screening period must be at least 2 weeks long and no more than 4 weeks long.
- c. For subjects who discontinue prematurely from the study or who do not enroll in the open-label extension study, a follow-up safety assessment will be conducted by telephone call approximately 30 days after the last dose of study drug.
- d. NPI-C combined agitation and aggression domain score and wash-out of prohibited medications are the only eligibility assessments required at both Screening and Baseline (Day 1). All other eligibility criteria are to be established during Screening.
- e. Height is assessed as part of the vital sign measurement only at the Screening Visit; weight will be assessed at every clinic visit as part of the vital sign measurements.
- f. 12-lead ECG to be completed in triplicate at screening and single read at subsequent visits. ECGs can be performed any time before blood sampling or at least 30 minutes after blood sampling during clinic visits.
- g. Urinalysis requirement not applicable to subjects who are unable to provide urine sample (e.g., incontinent subjects).
- h. A serum pregnancy test should be performed at the initial screening visit. A urine pregnancy test should be performed at Baseline (Day 1), Week 4, and Week 12 (EOS/ET) for female subjects of childbearing potential.
- i. Note: If collection at Week 2 does not occur, then collection should be attempted at Week 8.
- j. Only the agitation and aggression domain will be completed at the Screening Visit.
- k. MRI or CT must be obtained during or subsequent to diagnosis of probable AD, or during the screening period (prior to Baseline).
- l. Any untoward medical occurrence that occurs after signing the informed consent form (i.e., during the screening period) should be recorded as an adverse event, even if dosing has not begun.
- m. The first dose of study drug must be administered to the subject at the clinic only after all Baseline assessments are performed, including the blood sampling for PK assessment. If any Baseline assessments extend to an additional day, the first dose of study drug will be administered at completion of assessments on this day.

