5.3 Analysis Visit Windows

Baseline will be defined as the last non-missing result, including results from repeated and unscheduled measurements, before dosing.

Efficacy, safety, and PK assessments will be summarized by analysis visit as presented in Table 4 below.

Table 4 Analysis Visit Windows

Analysis Visit Name	Target Study Day ¹	Study Day Interval
Baseline	1	≤ 1
Week 2	15	2 to 21
Week 4	29	22 to 42
Week 8	57	43 to 70
Week 12	85	71 to 99
Follow-up	115	≥ 100

¹ study day = assessment date - first dose date + 1 if the assessment date \geq first dose date, otherwise study day = assessment date - first dose date. Study day 1 is the day of first administration of study drug (pimavanserin or placebo).

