5.3.2 Multiple Measurements within Visit Windows

If more than one assessment falls within a given window then the assessment closest to the target study day will be selected for the by-visit summaries. If two assessments are equidistant from the target day then the chronologically last assessment will be used for summary. Exceptions may be made for incomplete assessments, in which case, more complete assessments may be given priority. Details are provided in a separate programming conventions document.

For safety summaries where the most extreme values should be selected, e.g. overall post-Baseline minimum, overall post-Baseline maximum and potentially clinically important values, all non-missing post-Baseline values should be considered, regardless of if the value is selected for the by-visit summaries. All results will be presented in data listings.

When ECG is collected in triplicate, the average of the triplicate will be considered as one assessment for the summaries.

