15 CLINICAL PHARMACOKINETIC AND PHARMACODYNAMIC ANALYSES

For pimavanserin-treated subjects in the Pharmacokinetics Analysis Set, plasma concentration data for pimavanserin and its metabolite (AC-279) will be listed and summarized using descriptive summary statistics by visit and treatment group.

Concentrations that are below the limit of quantification (BLQ) will be displayed as "BLQ" in the data listings and imputed as 0 for computing summary statistics.

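### PK samples enter the by-visit tables by study day alone, so an off-drug or first-days sample can count as a visit concentration when no scheduled sample is closer to target

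*SAP*

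**What the plan says.** SAP 5.3 brings PK under the general visit windows: "Efficacy, safety, and PK assessments will be summarized by analysis visit as presented in Table 4 below". Table 4 counts days from the first dose:

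- Week 2: Days 2 to 21, target 15
- Week 4: Days 22 to 42, target 29
- Week 8: Days 43 to 70, target 57
- Week 12: Days 71 to 99, target 85

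SAP 5.3.1 sets eligibility: "Both scheduled and unscheduled assessments, including early termination visits, will be considered for planned timepoint summaries". SAP 5.3.2 then chooses within a window: "the assessment closest to the target study day will be selected for the by-visit summaries", with ties going to the later one. The only exception it mentions is for incomplete assessments. SAP 15 has concentrations "listed and summarized using descriptive summary statistics by visit and treatment group", with values below quantification set to 0 in the statistics. The PK Analysis Set (SAP 4) is defined per subject, so it removes no individual sample.

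Protocol 6.3 schedules PK at Baseline and Weeks 2, 4 and 12. Week 8 is only a make-up: "If collection at Week 2 does not occur, then collection should be attempted at Week 8". Extra draws follow certain events, where feasible: "blood samples will be collected from subjects who experience an SAE or an AE leading to discontinuation, as soon as possible after experiencing the event". Protocol 3.2.6 also lists "Blood sampling for PK assessments" at the combined end-of-study and early-termination visit. For every PK sample, "the actual dates and times of administration of the last 3 doses of study drug before PK sample collection will be recorded", if known.

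**The concern.** A by-visit concentration table is normally read as exposure on treatment at that time. The Table 4 windows measure time since the first dose. They say nothing about time since the last dose, which largely determines the level once a subject has stopped. The protocol plans two sample types, early-termination and event-triggered, that may be drawn after stopping, and the SAP makes both eligible.

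Plasma concentration of pimavanserin and AC-279 is the only PK endpoint, and this table is the only PK tabulation planned. An off-drug value, particularly one entered as 0, lowers the mean and widens the spread, and nothing in the table would show the reader that this had happened. The dose times that would identify such samples are collected, but the SAP gives them no role in the summary.

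**Working it through.** The plan states no figure to reproduce. The check traces the rule and then illustrates size under stated assumptions.

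**1. Apply Table 4 and SAP 5.3.2 to example sampling days.**

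| PK samples available (study day) | Result |
|---|---|
| ET on 8 only | Day 8 becomes Week 2 |
| Event sample on 5, Week 2 missed, scheduled 29 | Day 5 becomes Week 2 |
| Scheduled 15 and 29, ET on 60 | Day 60 becomes Week 8 |
| Scheduled 15, 29 and 85, event sample on 50 | Day 50 becomes Week 8 |
| Scheduled 15 and 29, ET on 75 | Day 75 becomes Week 12 |
| Scheduled 15 and 29, event sample on 20 | Not used |
| Scheduled 15 and 29, ET on 35 | Not used |

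An unscheduled sample never displaces a scheduled one taken on the target day. If the scheduled sample is 3 days late, an unscheduled one wins only on the 5 days from target −2 to target +2. If it is 3 days early, the tie at target +3 also goes to the later sample, making 6 days. The rule therefore filters well when a scheduled sample exists, and not at all when none does.

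**2. Build-up.** The documents give no half-life. Assume 24 to 96 h, first-order kinetics, once-daily dosing and a pre-dose draw. The fraction of the steady-state pre-dose level on Day d is 1 − 2^(−24(d−1)/t½).

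| Day | 24 h | 48 h | 72 h | 96 h |
|---|---|---|---|---|
| 2 | 50% | 29% | 21% | 16% |
| 5 | 94% | 75% | 60% | 50% |
| 8 | 99% | 91% | 80% | 70% |
| 15 | 100% | 99% | 96% | 91% |

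By Day 15 the shortfall is at most 9% over this range. The Week 4 window opens on Day 22, so for a continuously dosed subject build-up matters only in the Week 2 window.

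**3. Washout.** Under the same assumptions, the fraction left after k extra days off drug is 2^(−24k/t½).

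| Extra days off | 24 h | 48 h | 72 h | 96 h |
|---|---|---|---|---|
| 3 | 12% | 35% | 50% | 59% |
| 7 | 1% | 9% | 20% | 30% |

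Washout can affect any window. The follow-up contact is by telephone, so off-drug samples come only from ET visits, event-triggered draws or dose interruptions.

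**4. Shift in an arm mean.** If m of n samples sit at fraction f of the on-treatment level, the mean falls by m(1 − f)/n. With 111 randomized 1:1:1, n is about 111/3 = 37 if every subject contributes. The values of m and f below are assumptions.

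- m = 3: from 3 × 0.5/37 = 4.1% (f = 0.5) to 3 × 1/37 = 8.1% (f = 0)
- m = 5: from 5 × 0.5/37 = 6.8% to 5 × 1/37 = 13.5%

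The shift varies as 1/n, so each affected sample weighs more in a Week 8 row, where few samples are expected.

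**The case against.** The strongest reply is that these samples are only considered and must then win on distance to target. This stands for subjects who attend their scheduled draws. A reader might infer that all event-triggered and ET samples flow into the means, or that they are often alone in their window. The documents give no dropout rate, event rate or sample count that would support either inference.

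A reader might also take every ET sample to be off drug. Protocol 5.9.5 has dosing continue to the Week 12 (EOS/ET) visit, and SAP 5.4 substitutes that visit's date when the last dose date is missing. Dosing up to the visit is therefore the default, and a serious event need not mean stopping. The documents still set no maximum gap between last dose and ET visit, so some ET samples can be off drug.

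A distorted comparison of 34 mg with 20 mg is a further tempting inference. No formal exposure comparison or exposure-response analysis is planned, and nothing shows that early stopping will differ by arm.

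Finally, all data will be listed, and the table specifications and programming conventions are separate documents not seen here. Whether a Week 8 PK row will be produced is thus open. Listings let a careful reader find the affected values, but they do not correct the summary statistics.

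**Conclusion.** The point holds in a limited form. As written, the SAP can report an off-drug sample as an on-treatment visit concentration in any window, and a first-days sample as Week 2, whenever no scheduled PK sample lies closer to target. This follows from rules the SAP states, which name PK explicitly, and not merely from missing detail.

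The size cannot be derived from the documents. The illustrated falls of 4% to 13.5% in an arm mean rest on an assumed 3 or 5 affected samples out of 37, at 0 to 50% of the on-treatment level. They are not a forecast. The half-life range and the pre-dose draw in the build-up table are also assumptions, since after Baseline the protocol does not require pre-dose PK sampling.

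The consequence is likely modest. PK is exploratory and descriptive in a study stopped at 111 subjects with no hypothesis tests, and no efficacy or safety result depends on these means. It is still worth correcting, because the table is the sole PK summary and the information needed is already collected.

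**What to change.** In SAP 15, exempt PK from section 5.3.1 and state that:

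- By-visit concentration summaries use scheduled samples from subjects still on study drug at the draw. Week 8 samples taken to replace a missed Week 2 draw are included and labelled as make-up samples.
- On-drug status is judged from the recorded dose times, not from the last dose date imputed under SAP 5.4, using a time-since-last-dose limit that the sponsor sets before unblinding. The documents provide no basis for a particular limit, so the sponsor should justify the one chosen.
- Off-drug ET samples, samples triggered by an SAE or a discontinuing AE, and samples with unknown dose time go into a separate listing with time since last dose.
- The all-samples table may be kept as a secondary display.

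This needs a few lines of text and one variable derived from data already on the CRF. Protocol 9.9 asks only for listing and descriptive summary, so the change does not conflict with it. Concentrations stay blinded until the database is unblinded, so the rule can be fixed without sight of results. The downside is slightly fewer samples per cell.

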5.3.2 Multiple Measurements within Visit Windows

If more than one assessment falls within a given window then the assessment closest to the target study day will be selected for the by-visit summaries. If two assessments are equidistant from the target day then the chronologically last assessment will be used for summary. Exceptions may be made for incomplete assessments, in which case, more complete assessments may be given priority. Details are provided in a separate programming conventions document.

For safety summaries where the most extreme values should be selected, e.g. overall post-Baseline minimum, overall post-Baseline maximum and potentially clinically important values, all non-missing post-Baseline values should be considered, regardless of if the value is selected for the by-visit summaries. All results will be presented in data listings.

When ECG is collected in triplicate, the average of the triplicate will be considered as one assessment for the summaries.

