### **6.2.7 Clinically Significant Abnormalities**

Laboratory abnormalities judged by the Investigator to be clinically significant will be repeated as clinically appropriate. Abnormal laboratory test results that are considered to be clinically significant by the Investigator may be recorded as an AE.

Laboratory results will be reported to the Investigator who will review abnormal laboratory findings for clinical significance. Further details on blood and urine sample collection are specified in the laboratory manual.

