14.4 Electrocardiogram (ECG)

Electrocardiogram is performed at Screening, Baseline, Weeks 4 and 12/ET visits. All tracings will be evaluated by a central reading laboratory. ECG data summaries will be performed using the centrally evaluated data.

Observed values of ECG variables (heart rate, PR interval, RR interval, QRS interval, QT interval, and QTc intervals) and the changes from Baseline at each assessment timepoint will be summarized by treatment group at Baseline, Week 4, and Week 12 visits.

QTc intervals include QTcB (Bazett's formula) and QTcF (Fridericia's formula). QTcF will also be categorized into the following categories (msec) and the number and percentage of subjects in each category will be summarized by treatment group at each visit and overall post-Baseline maximum:

- Observed: ≤450, 451 to 480, 481 to 500, and >500
- Change from Baseline: ≤10, 11 to 30, 31 to 60, and >60

Electrocardiogram variable values will be considered PCI if they meet or exceed the upper limit values listed in Table 8. The number and percentage of subjects with post-Baseline PCI values will be summarized by treatment group at each post-Baseline visit and for overall post-Baseline. For the overall post-Baseline summaries, all post-Baseline values will be considered, including unscheduled and out of window values. Subjects with multiple PCI values for a given parameter will be counted only once for that parameter. For the by-visit summary, the numerator for the percentage is the number of subjects with a post-Baseline PCI ECG for the given parameter, visit and treatment group and the denominator is the number of subjects with non-missing values for the given parameter, visit and treatment

group. For the overall post-Baseline summary, the numerator for the percentage is the number of subjects with at least 1 post-Baseline PCI ECG for the given parameter and treatment group and the denominator is the number of subjects with at least 1 post-Baseline ECG value for the given parameter and treatment group. A listing of all subjects with any PCI values will be provided.

Table 8 Criteria for Potentially Clinically Important ECG Values

ECG Parameter	Unit	High PCI Criteria
QRS Interval	msec	≥120
PR Interval	msec	≥220
QTcB or QTcF	msec	>500
QTcB or QTcF: change from Baseline	>60 msec	

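### SAP 5.3 gives scheduled results no priority over unscheduled repeats, so by-visit safety summaries can be biased towards normal where a repeat is prompted by an abnormal value

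*SAP*

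**What the plan says.** Three rules in SAP 5.3 act together.

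- **Eligibility (5.3.1).** "Both scheduled and unscheduled assessments, including early termination visits, will be considered for planned timepoint summaries". No lower rank is given to unscheduled results.
- **Selection (5.3.2).** When a window holds several results, "the assessment closest to the target study day will be selected for the by-visit summaries". On a tie, "If two assessments are equidistant from the target day then the chronologically last assessment will be used for summary".
- **Distance (5.3, Table 4 footnote).** Study day is a difference of dates ("study day = assessment date - first dose date + 1 if the assessment date" is on or after first dose), so clock time plays no part.

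The one stated exception is discretionary: "Exceptions may be made for incomplete assessments, in which case, more complete assessments may be given priority". Its details are left to a separate programming document.

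On what prompts a repeat, Protocol 6.2.7 says: "Laboratory abnormalities judged by the Investigator to be clinically significant will be repeated as clinically appropriate". Neither document states a trigger for repeating a vital sign or an ECG.

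SAP 5.3.2 also contains a safeguard. Overall post-Baseline minimum and maximum and PCI summaries draw on every non-missing post-Baseline value, selected or not, and all results are listed. For QTcF categories, SAP 14.4 says "the number and percentage of subjects in each category will be summarized by treatment group at each visit and overall post-Baseline maximum", so there is a by-visit version and an overall version.

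**The concern.** Choosing by nearness to target looks neutral because it ignores the value itself. It is not neutral if the existence of a second result depends on the first. A laboratory value judged clinically significant is to be repeated, and nothing asks for a normal one to be repeated. If the repeat then displaces the scheduled result, high values are replaced by values that have on average moved back, through recovery or regression to the mean.

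The outputs exposed are by-visit means and changes for laboratory tests, vital signs and ECG, by-visit laboratory shift tables, and by-visit QTcF categories. An arm with more abnormal values would have more repeats and so more replacement, which would narrow a true difference between arms. An abnormal value could appear in an overall table and in no by-visit table.

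Safety is reported descriptively, and Protocol 1.2 cites an average QT prolongation of about 5-8 ms. With 111 subjects in three arms (111/3 = 37), reclassifying one subject moves a by-visit percentage by 1/37 = 2.7 points.

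**Working it through.** The documents give no figure for this point, so there is none to reproduce. Two checks were made.

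**1. When does a repeat displace the scheduled result?**

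Inputs: target Day 29 (Week 4) or Day 85 (Week 12), analysis windows Days 22-42 and 71-99 (SAP Table 4), and a visit window of plus or minus 3 days (SAP Table 1). For a scheduled visit on day s and a repeat k days later, with target t, the repeat is used if |s + k - t| <= |s - t|. Both results are taken as complete, with no third result nearer the target.

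| Repeat lag k (days) | 0 | 1 | 2 | 3 | 4 | 5 | 6 | 7 |
|---|---|---|---|---|---|---|---|---|
| In-window visit days (of 7) on which the repeat is used | 7 | 3 | 3 | 2 | 2 | 1 | 1 | 0 |

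The counts are the same for Weeks 4 and 12. Example: a visit on Day 26 is 3 days from Day 29, so any repeat up to Day 32 (k = 6) is used. A later-day repeat never displaces a visit on or after the target day.

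**2. How large could the bias be?**

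Assumptions, none in the documents: values standardised to SD 1 and normal; correlation rho = 0.5 to 0.9 between a subject's two readings; a repeat only when the first exceeds a cut-off c = 1.645 to 2.5; and every repeat replaces the first. This is an upper-end scenario.

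Mean shift = -(1 - rho) x phi(c), where phi is the normal density.

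- Largest: rho = 0.5, c = 1.645: 0.5 x 0.103 = 0.052 SD towards normal.
- Smallest: rho = 0.9, c = 2.5: 0.1 x 0.0175 = 0.002 SD.

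The simulation (2,000,000 draws per setting) agreed with the formula. At c = 1.96 it gave these by-visit abnormal rates, with the active arm shifted by 0.30 SD for the last column:

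| rho | Rate, first reading | Rate, after replacement | Between-arm rate difference, before to after |
|---|---|---|---|
| 0.5 | 2.5% | 0.5% | 2.35 to 0.70 points |
| 0.7 | 2.5% | 0.8% | 2.34 to 1.06 points |
| 0.9 | 2.5% | 1.5% | 2.35 to 1.60 points |

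Over all settings, the true mean difference of 0.30 SD became 0.27 to 0.30 SD.

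On a QTcF scale, assume a mean of 425 ms, between-subject SD 18 and within-subject SD 8 to 12, with every tracing above 450 ms repeated the same day. The total SD is sqrt(18² + 8²) = 19.7 to sqrt(18² + 12²) = 21.6 ms. The share above 450 ms falls from 10.2-12.4% to about 6.1-6.2%, and the mean falls by 0.6-1.4 ms. If only half of those tracings are repeated, the effect is about half.

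**The case against.** The strongest objection is that the documented trigger and the same-day route do not meet. Protocol 6.2.7 covers laboratory tests, and Protocol 6.2.6 sends these to a central laboratory, so a repeat prompted by the result will normally come days later. The same-day route is realistic mainly for vital signs and ECG, for which no trigger is stated. SAP 14.4 also uses centrally read ECGs. This stands, and it limits the documented laboratory case mainly to visits before the target day.

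A reader might infer that a same-day repeat always wins, that only abnormal values are overwritten, and that laboratory, vital-sign and ECG tables are all shifted. The documents do not support this:

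- The incomplete-assessment exception could keep a full scheduled panel over a one-analyte repeat, and a third result could lie nearer the target.
- Unscheduled results also come from discretionary safety testing (Protocol Table 6-1), contacts after a serious event (Protocol 7.6.1) and early termination visits (SAP 5.3.1). Some may be more abnormal than the scheduled value.
- No repeat frequency or timing is given, so an actual shift cannot be shown.

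The safeguards are also substantial. Overall extremes, shifts to the overall minimum and maximum, and QTcF at overall maximum all keep the first value. Baseline is the last pre-dose result, repeats included, so changes from Baseline may be partly offset. The assumed QTcF mean shift of 0.6-1.4 ms is well below the standard error of an arm mean (19.7/sqrt(37) = 3.2 to 21.6/sqrt(37) = 3.6 ms).

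What remains is that no stated rule protects the by-visit means, by-visit laboratory shifts or by-visit QTcF categories. The incomplete-assessment exception would not stop a complete repeat ECG or blood pressure from being selected.

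**Conclusion.** The concern holds in a limited, conditional form. The selection rule lets an unscheduled repeat displace a scheduled result, and where an abnormal value prompted the repeat, the expected bias is towards normal. For laboratory tests this arises mainly when the scheduled visit was early, on at most 3 of 7 in-window days. For vital signs and ECG, the same-day route works on all 7 days, but the trigger is an assumption.

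Overall minimum, maximum and PCI summaries are protected. By-visit PCI counts are unclear: SAP 5.3.2 names PCI values without restriction, while SAP 14.2 to 14.4 mention unscheduled values only for the overall counts.

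The actual size is unknown. Under the assumptions above, the effect on means is small (0.002 to 0.052 SD), while the relative effect on by-visit abnormal categories can be larger. It is worth correcting because these tables are descriptive safety evidence in arms of about 37, and the correction is simple.

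**What to change.** Add to SAP 5.3.2, for by-visit safety summaries only:

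- Select the scheduled assessment in the window.
- Use an unscheduled result only when no valid scheduled value exists.
- When a scheduled test is repeated the same day, keep the first valid reading. A reading recorded as technically invalid may be replaced.

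Leave the all-values rule for extremes and PCI unchanged, and state whether it covers by-visit PCI counts.

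With this rule, no valid scheduled result is displaced by a repeat, and the shift under the assumptions above is zero. The cost is a short addition to the SAP and a selection flag in programming, which needs invalid readings to be identifiable in the data. By-visit abnormal rates may come out slightly higher.
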